9.1.2 Open-label Treatment Period

Approximately 500 patients are planned for enrollment in the OLTP; all patients will receive open-label rapastinel at 450 mg IV (adjunctive to ADT), either weekly or once every 2 weeks, based upon the Investigator's discretion. Patients will skip odd-numbered visits if being treated on a biweekly basis). The once-every-2-weeks schedule can only be initiated on even-numbered visits in order to maintain the appropriate visit schedule. Patients who are on a once-every-2-weeks schedule can be transitioned back to weekly visits at any visit.

Upon completion of the OLTP at Visit 54 (Week 52, ET), patients will enter a 2-week safety follow-up period and will return to the clinic at Visit 55 (Week 54). The maximum duration of the study will be 56 weeks.

The study will be terminated when 100 patients have completed the 52-week OLTP.

9.1.3 Safety Follow-up Period

All patients who complete or discontinue from the OLTP should enter the 2-week safety follow-up period.

Additional follow-up visits may be scheduled within 30 days, if necessary, for safety reasons.

9.2 DISCUSSION OF STUDY DESIGN, INCLUDING THE CHOICE OF CONTROL GROUPS

The 52-week, open-label study was designed to assess long-term safety following continued adjunctive rapastinel treatment in adult patients with MDD. In this study, investigators will enroll patients who completed Study RAP-MD-04 or, as needed, enroll patients 18 through 65 years of age who meet the Diagnostic and Statistical Manual of Mental Disorders, Fifth Edition (DSM-5) criteria for MDD ([American Psychiatric Association, 2013](#)). The MDD diagnosis will be confirmed using the Modified Structured Clinical Interview for Diagnostic Statistic Manual of Mental Health Disorders, Fifth Edition (SCID). The symptoms and severity of MDD will be assessed using the Montgomery-Åsberg Depression Rating Scale (MADRS) ([Section 9.5.1.2.1](#)).

Study centers will have experience with the study population and will be encouraged to apply available guidelines to minimize patient risk or distress.

Dose selection information is presented in [Section 9.4.6](#). The planned dosing regimen is based on experience from previous rapastinel studies.

The 2-week safety follow-up period allows continued patient monitoring after IP has been discontinued.

9.3 SELECTION OF STUDY POPULATION

9.3.1 Inclusion Criteria

Note: For rollover patients who completed the lead-in study (RAP-MD-04), medical, psychiatric, and medication histories from Visit 1 of RAP-MD-04 will be used. For such patients, Inclusion Criteria 2, 4, 5, and 6 are not applicable based on participation in RAP-MD-04.

To be eligible to participate in the study, patients must meet the following criteria:

1. Written informed consent, obtained from the patient before the initiation of any study-specific procedures ([Section 5.3](#))
2. Male or female outpatients who are 18 to 65 years of age
3. For rollover patients from RAP-MD-04, completion of Study RAP-MD-04 (either OLTP or DBTP) with continued ADT treatment
4. Meet DSM-5 criteria for MDD based on confirmation from the modified SCID, with a current major depressive episode of at least 8 weeks and not exceeding 18 months in duration at Visit 1

6. Have no more than partial response (< 50% improvement) to ongoing treatment with a protocol-allowed ADT

8. If female of childbearing potential, have a negative serum β -human chorionic gonadotropin (β -hCG) pregnancy test at Screening (Visit 1). Because Visit 1 pregnancy test results will not be available on the day of Visit 1, rollover patients can be discontinued at Visit 2 if Visit 1 pregnancy test is positive.

9.3.2 Exclusion Criteria

Note: For rollover patients who completed the lead-in study (RAP-MD-04), medical, psychiatric, and medication histories from Visit 1 of the lead-in study will be used (Exclusion Criteria Nos. 1-8, 12-14, 17, 21-25, and 27). Because Visit 1 clinical laboratory or ECG results will not be available on the day of Visit 1, if there are any safety concerns related to Visit 1 clinical laboratory or ECG results, patients can be discontinued at Visit 2.

Patients who meet any of the following criteria will not be eligible to participate in the study:

Exclusion criteria to be assessed at Screening (Visit 1)

Psychiatric and Treatment-Related Criteria:

1. DSM-5-based diagnosis of any disorder other than MDD that was the primary focus of treatment within 6 months before Visit 1. Comorbid generalized anxiety disorder, social anxiety disorder, or specific phobias are acceptable provided they play a secondary role in the balance of symptoms and are not the primary driver of treatment decisions.
2. Lifetime history of meeting DSM-5 criteria for:
 - Schizophrenia spectrum or other psychotic disorder
 - Bipolar or related disorder
 - Major neurocognitive disorder
 - Neurodevelopmental disorder of greater than mild severity or of a severity that impacts the patient's ability to consent, follow study directions, or otherwise safely participate in the study
 - Dissociative disorder

- Screen failure (failure to meet inclusion/exclusion criteria)
- Pregnancy
- Withdrawal of consent
- AE
- Lack of efficacy
- Protocol violation
- Noncompliance with IP
- Noncompliance with ADT
- Lost to follow-up
- Study terminated by Sponsor
- Study center terminated by Sponsor
- Other

All patients who prematurely discontinue from the study, regardless of cause, should be seen for a final assessment at an ET Visit. A *final assessment* will be defined as completion of the evaluations scheduled for all patients at Visit 54 (Week 52). All patients discontinuing the study prematurely should enter the 2-week safety follow-up period.

Patients who discontinue from the study and do not return to the study center for final assessments must be requested in writing to return to the study center for a final assessment. A copy of the letter, together with the source documentation, will be kept in the Investigator's files. The reason for premature discontinuation from the study will be recorded on the Study Termination Page of the eCRF. Study center staff will be contacted by the Sponsor after each premature discontinuation to ensure proper characterization of the reason for discontinuation is captured.

9.3.4 Patient Replacement Procedures

Patients in this study who prematurely discontinue treatment will not be replaced.

9.4 TREATMENTS

During the OLTP, all eligible patients will receive open-label, once-weekly or once every 2 weeks (biweekly, at Investigator's discretion) IV rapastinel 450 mg. Patients receiving biweekly treatment will skip all odd-numbered visits on the Schedule of Evaluations (Section 2.0).

9.4.1 Background Antidepressant Therapy

De novo patients must enter the study while having no more than partial response (< 50% improvement) to ongoing treatment with a protocol-allowed ADT [REDACTED]

[REDACTED]

Patients entering from Study RAP-MD-04 will have already fulfilled this requirement but must continue their background ADT as described below.

Upon entry into the study at Screening/Visit 1, the dosage of the ADT must be held constant at a dose in accordance with the respective label throughout participation in RAP-MD-06. If a patient experiences an AE, intercurrent illness, or symptoms of intolerance, he or she will be permitted to stop taking the ADT for a maximum of 5 consecutive days at the discretion of the Investigator. No other alterations in the ADT dose regimen are allowed. If an ADT dose change is required during the study, the patient should be discontinued from the study.

Background ADT medication compliance will also be closely monitored. Compliance will be based on patient report. Every effort should be made to have patients bring their background ADT to each study visit for verification of patient-reported compliance by pill count (to the extent possible).

9.4.2 Treatments Administered

The IP will only be administered to eligible patients under the supervision of the Investigator or identified subinvestigators or other assigned personnel authorized to administer IV drugs. IP will be administered in a “slow bolus” injection to an upper extremity vein within approximately 1 to 2 minutes to each study patient. The patient should not be discharged from the study center until the Investigator or medically qualified subinvestigator determines that the patient is medically able to leave the study center (recommended not less than 15 minutes following administration).

9.4.3 Identity of Investigational Product

Rapastinel 450 mg IV Prefilled Syringes: [REDACTED]

The study center personnel will complete the kit label and attach the tear-off portion from the kit label to the source documents.

The prefilled syringe will be labeled with the protocol number and kit number. The study center personnel will write the PID number on the prefilled syringe associated with the kit mentioned above. The prefilled syringe will not have a tear-off and the label will remain on the prefilled syringe.

9.4.4 Handling of Investigational Product

The IP must be stored in a secure area and administered only to patients entered into the clinical study, at no cost to the patient, in accordance with the conditions specified in this protocol.

At the end of the study, all IP must be accounted for. In addition, at the end of the study, all unused IP and empty IP packages should be returned to the Sponsor or the local distributor at the address provided in the Study Reference Manual.

9.4.5 Method of Assigning Patients to Treatment Groups

Patients enrolling from RAP-MD-04 will keep the same PID number that was assigned in that study.

For *de novo* patients (new patients who did not participate in RAP-MD-04), after a patient signs the ICF at Screening (Visit 1), study personnel will register the patient in the IWRS, and the system will assign the patient a sequential PID number. [REDACTED]

The IP will be labeled with medication kit numbers. The IWRS will provide the study center with the specific medication kit number(s) for each patient. Study centers will dispense IP according to the IWRS instructions. Study centers will also log onto the IWRS at subsequent visits to obtain a study medication kit number for dispensing IP. Study centers will receive the IWRS confirmation notifications for each transaction. All notifications are to be maintained with the study source documents.

9.4.6 Selection of Dosages in the Study

A rapastinel dose of 450 mg was chosen for this study based on results from 2 Phase 2 clinical studies of patients with MDD in which single IV doses of rapastinel 5 mg/kg and 10 mg/kg were shown to produce marked antidepressant effects within 1 day that lasted approximately 1 week or longer in responding patients. The 450-mg IV dose is expected to provide an appropriate dose for most patients based upon the Phase 2 study results. The use of a single-unit dose is intended to aid in the simplicity of administration and avoid dosing errors.

RAP-MD-04 also assessed both weekly and biweekly dosing regimens. While the GLYX13-C-202 study also assessed the effect of weekly and biweekly administration after initial stabilization, and found no differences, the comparison was only carried out for 6 weeks in that study. Assessing a less frequent dosing regimen over the more substantial time period of 26 weeks to 2 years in RAP-MD-04 followed by an additional 52 weeks of treatment in RAP-MD-06 is expected to yield a better understanding of the long-term safety characteristics of rapastinel treatment and allow proper guidance to physicians regarding treatment beyond initial stabilization.

9.4.7 Selection and Timing of Dose for Each Patient

The IP will be administered IV using the assigned single-use prefilled syringes either weekly or biweekly based on the discretion of the Investigator, per the Schedule of Evaluations ([Section 2.0](#)). A patient may be switched between weekly and biweekly treatment at any time during the OLTP. For patients on a biweekly schedule, only odd-numbered visits during the OLTP may be skipped.

9.4.7.1 Screening Period

For patients enrolling from RAP-MD-04, the final visit from that study (Visit 122 [Week 104, ET]) will serve as Visit 1 in this study, after written consent is obtained. Rollover patients will receive open-label IP at Visit 1 to ensure continuity of treatment.

For *de novo* patients, at Visit 1, after written consent is obtained, patients will enter a screening period of up to 14 days. No IP is administered to *de novo* patients during the screening period; however, patients must continue their background ADT at a stable dose. During this time *de novo* patients will wash out of prohibited medications, per [Appendix III](#).

9.4.7.2 Open-label Treatment Period

Patients enrolling from RAP-MD-04 who meet all eligibility criteria at Screening (Visit 1) will receive IP at Visit 1, and patients who continue to meet all the eligibility criteria for participation in the study at Baseline (Visit 2) will continue to receive IP during the OLTP.

De novo patients who meet all eligibility criteria at Screening (Visit 1) and who continue to meet all the eligibility criteria for participation in the study at Baseline (Visit 2) will be assigned an IP kit number via IWRS at Visit 2.

All eligible patients will receive rapastinel 450 mg IV from a prefilled single-dose syringe at Visits 2 through Visit 53 (Week 51).

9.4.7.3 Safety Follow-up Period

Patients who complete the OLTP or patients who prematurely discontinue from the study should enter the 2-week safety follow-up period, returning to the clinic for Visit 55 (Week 54). No IP is administered during the safety follow-up period. Patients' background ADT may be modified as deemed appropriate by the Investigator.

9.4.8 Blinding

Not applicable

9.4.9 Unblinding

Not applicable

9.4.10 Prior and Concomitant Therapy

A list of example medications that are allowed and not allowed as concomitant medications for either episodic or chronic use is provided in [Appendix III](#).

For *de novo* patients, medication history (psychotropic medication history during the previous 5 years and all other medications during the past 12 months) will be recorded at Screening (Visit 1) in the eCRF. Thereafter, any changes in concomitant medications or any new medications added will be recorded in the eCRF.

[REDACTED]

[REDACTED]

[REDACTED]

[REDACTED]

[REDACTED]

[REDACTED]

[REDACTED]

[REDACTED]

[REDACTED]

For women of childbearing potential who may participate in the study, the following methods of contraception, if properly used, are generally considered reliable: hormonal contraceptives (ie, oral, patch, injection, implant), male condom with intravaginal spermicide, diaphragm or cervical cap with spermicide, vaginal contraceptive ring, intrauterine device, surgical sterilization (bilateral tubal ligation, bilateral salpingectomy), vasectomized partner, or sexual abstinence.

The Investigator and each patient will determine the appropriate method of contraception for the patient during the participation in the study.

See [Section 9.5.2.3](#) for pregnancy reporting procedures.

9.4.12 Monitoring Treatment Compliance

IP compliance during any period will be closely monitored by capturing the date and time of each injection of IP. If a scheduled injection does not occur, the Sponsor must be notified and the reason captured in the eCRF.

Background ADT compliance will also be closely monitored. Background ADT medication compliance will be based on patient report. Every effort should be made to have patients bring their background ADT to each study visit for verification of patient-reported compliance by pill count (to the extent possible). Missed doses or other changes in the dose of ADT and the reason should be captured in the eCRF.

9.4.13 Treatment After Discontinuation

Patients whose MDD symptoms worsen or are determined by the Investigator not to be adequately controlled prior to completing the OLTP will be allowed to discontinue the study and start appropriate treatment at the Investigator's discretion. This new treatment will not be provided by the Sponsor. Patients who initiate a new treatment must be discontinued from the study.

9.5 EFFICACY AND SAFETY VARIABLES

9.5.1 Diagnostic and Efficacy Assessments

9.5.1.1 Diagnostic Assessments

The SCID will be administered during the screening interviews by a psychiatrist, doctoral level clinical psychologist, or other clinician who has extensive professional training and experience in the diagnosis of mental illness and who meets the training requirements and qualifications standards set by the Sponsor and rater training vendor.

[REDACTED]

[REDACTED]

[REDACTED]

9.5.2 Safety Assessments

Patients must be evaluated by a physician or an appropriately-trained healthcare professional at every visit and the evaluation must be documented. The procedures discussed in the following sections will be completed at the designated visits.

9.5.2.1 Adverse Events

An AE is any untoward medical occurrence in a patient or clinical investigation patient administered a pharmaceutical product and which does not necessarily have to have a causal relationship with this treatment. An AE can therefore be any unfavorable and unintended sign (including an abnormal laboratory finding, for example), symptom, or disease temporally associated with the use of a medicinal product, whether or not considered related to the medicinal product (ICH-E2A).

For the purpose of the study center's data collection responsibilities, any untoward event that was reported from the time the patient signed the ICF until 30 days after the final protocol-defined study visit or the last known dose of IP (if the final visit does not occur) is to be considered an AE.

Examples of AEs are as follows:

- Changes in the general condition of the patient
- Subjective symptoms offered by or elicited from the patient
- Objective signs observed by the Investigator or other study center personnel
- All diseases that occur after signing informed consent, including any change in severity or frequency of pre-existing disease
- All clinically relevant abnormalities in laboratory values or clinically relevant physical findings that occur during the study schedule

Please note that medical procedures scheduled prior to consenting, but occurring during the study should not be captured as AEs, but should be listed in the medical history if related to a pre-existing condition.

9.5.2.1.1 Causality Assessment

For each AE, the Investigator must provide an assessment of causal relationship to the IP. The causality assessment must be recorded on the appropriate AE reporting page of the patient's eCRF. Causal relationship must be assessed by answering the following question:

Is there a reasonable possibility the IP caused the event?

Yes: There is evidence to suggest a causal relationship between the IP and AE, ie:

- There is a reasonable temporal relationship between the IP and the event, and/or
- The event is unlikely to be attributed to underlying/concurrent disease or other factors, and/or
- Positive dechallenge and/or rechallenge exist

No: There is no evidence to suggest a causal relationship between the IP and AE, ie:

- There is no reasonable temporal relationship between the IP and the event, or

- The patient did not take the IP, or
- The event is likely to be attributed to underlying/concurrent disease or other factors, or
- The event is commonly occurring in the (study) population independent of IP exposure

9.5.2.1.2 *Severity Assessment*

The Investigator will provide an assessment of the severity of each AE by recording a severity rating on the appropriate AE reporting page of the patient's eCRF. *Severity*, which is a description of the intensity of manifestation of the AE, is distinct from *seriousness*, which implies a patient outcome or AE-required treatment measure associated with a threat to life or functionality ([Section 9.5.2.1.3](#)). Severity will be assessed according to the following scale:

- Mild:** A type of AE that is usually transient and may require only minimal treatment or therapeutic intervention. The event does not generally interfere with usual activities of daily living.
- Moderate:** A type of AE that is usually alleviated with additional specific therapeutic intervention. The event interferes with usual activities of daily living, causing discomfort, but poses no significant or permanent risk of harm to the research participant.
- Severe:** A type of AE that interrupts usual activities of daily living, or significantly affects clinical status, or may require intensive therapeutic intervention.

9.5.2.1.3 *Serious Adverse Events*

An SAE is any untoward medical occurrence that at any dose:

- Results in death
- Is life threatening
- Requires inpatient hospitalization or prolongation of existing hospitalization
- Results in persistent or significant disability/incapacity, or
- Is a congenital anomaly/birth defect

Important medical events that may not result in death, be life threatening, or require hospitalization may be considered serious when, based on appropriate medical judgment, they may jeopardize the patient and may require medical or surgical intervention to prevent one of the outcomes listed in this definition. Examples of such medical events include allergic bronchospasm requiring intensive treatment in an emergency room or at home, blood dyscrasias or convulsions that do not result in patient hospitalization, or the development of IP dependency or drug abuse.

Emergency room visits that do not result in hospitalization should be evaluated for one of the other serious outcomes to determine whether they qualify as SAEs.

Preplanned hospitalizations (eg, elective procedures for pre-existing conditions that did not worsen, such as cosmetic surgery and hysterectomy) are excluded from SAE reporting.

9.5.2.1.4 Reporting Adverse Events and Serious Adverse Events

At each visit, patients are to be queried regarding any AEs or SAEs that have occurred since the previous visit. Patients will be asked to volunteer information with a nonleading question such as, “How do you feel since your last visit?” Study center personnel will record all pertinent information in the patient’s eCRF.

All AEs must be recorded on the appropriate AE reporting page of the patient’s eCRF whether or not they are considered causally related to the IP.

For every AE, the Investigator must:

- Provide an assessment of the seriousness of the event (ie, is it an SAE?), as well as the severity and casual relationship
- Document all actions taken with regard to the IP
- Detail any other treatment measures taken for the AE
- Document the outcome of the AE

In addition, patients are to be reminded, as described in the ICF and in accordance with [Section 9.5.2.1](#), to notify study center personnel of any AEs occurring during the 30-day poststudy period. Any AEs reported by the patient (or patient representative) during this period are to be recorded in original source documents. AEs are also to be recorded in the eCRF if at least one of the following conditions is met: 1) the event meets the criteria for an SAE (see [Section 9.5.2.1.3](#) and [Section 9.5.2.1.4](#)), and/or 2) the event is judged by the Investigator to be potentially causally related to IP.

Any AEs that are ongoing at the time of the final protocol-defined study visit will be followed until the condition returns to prestudy status, has resolved or stabilized, or can be explained as being unrelated to the IP. If a follow-up visit is deemed necessary for appropriate safety surveillance, it will take place within 30 days of the final protocol-defined study visit.

9.5.2.2 *Immediate Reporting of Serious Adverse Events and Events of Special Interest*

The Sponsor is required to inform worldwide regulatory authorities of SAEs that meet specific criteria. Therefore, the Sponsor must be notified immediately regarding any SAE that occurs after informed consent is obtained.

Within 24 hours of learning of any AE that meets one of the criteria for an SAE, the study center personnel must report the event to Global Drug Safety on the SAE Form for Clinical Trials. The Study Physician may also be notified by telephone.

If, during follow-up, any nonserious AE worsens and eventually meets the criteria for an SAE, that AE should be recorded as a new SAE.

The study center must transmit the SAE Form for Clinical Trials to the SAE fax number provided at the end of this section. Even if an initial report is made by telephone, the SAE Form for Clinical Trials completed with all available details must still be faxed within 24 hours of knowledge of the event at the study center.

Supplemental information should be submitted as soon as available and may include laboratory results, radiology reports, progress notes, hospital admission and emergency room notes, holding and observation notes, discharge summaries, autopsy reports, and death certificates.

The Investigator is expected to take all therapeutic measures necessary for resolution of the SAE. Any medications or procedures necessary for treatment of the SAE must be recorded on the appropriate pages of the patient's eCRF. All SAEs are to be followed by the study staff until resolution or until the SAE is deemed stable. ***The Sponsor may contact the study center to solicit additional information or follow up on the event.***

Fax the SAE Form for Clinical Trials to the Sponsor.

[REDACTED]

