9.7.6 Safety Analyses

The safety analysis will be performed using the Safety Population, defined as all patients who receive at least 1 dose of IP during the OLTP.

The safety parameters will include AEs; clinical laboratory, vital signs, and ECG parameters; and the BPRS+, CADSS, [REDACTED].

For each safety parameter, the last assessment made before the first dose of open-label IP will be used as the baseline for *de novo* patients, and the baseline of the first lead-in study will be used as the baseline for rollover patients for all analyses of that safety parameter. Continuous variables will be summarized by number of patients and mean, SD, median, minimum, and maximum values. Categorical variables will be summarized by number and percentage of patients.

9.7.6.1 *Adverse Events*

AEs will be coded by system organ class (SOC) and preferred term using the *Medical Dictionary for Regulatory Activities*.

For rollover patients, an AE (classified by preferred term) that occurs during the OLTP will be considered a treatment-emergent adverse event (TEAE) if it was not present before the first dose of IP in the first lead-in study or was present before the first dose of IP in the first lead-in study and increased in severity during the OLTP. If more than 1 AE is reported before the first dose of IP in the first lead-in study and coded to the same preferred term, the AE with the greatest severity will be used as the benchmark for comparison with the AEs occurring during the OLTP that were also coded to that preferred term.

For *de novo* patients, an AE (classified by preferred term) that occurs during the OLTP will be considered a TEAE if it was not present before the first dose of open-label IP or was present before the date of the first dose of open-label IP and increased in severity after the first dose of open-label IP. If more than 1 AE is reported before the first dose of open-label IP and is coded to the same preferred term, the AE with the greatest severity will be used for comparison with the AEs occurring during the OLTP that were also coded to that preferred term.

An AE that occurs more than 30 days after the date of the last dose of IP will not be considered a TEAE.

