A TEAE occurring during the OLTP will be considered a newly emergent AE (NEAE) if the AE was not present before the first dose of open-label IP or was present before the first dose of open-label IP but increased in severity during the OLTP. The number and percentage of patients reporting NEAEs during the OLTP will be summarized by SOC and preferred term.

The number and percentage of patients reporting TEAEs will be tabulated by SOC and preferred term and further categorized by severity and causal relationship to the IP. If more than 1 AE is coded to the same preferred term for the same patient, the patient will be counted only once for that preferred term using the greatest severity and strictest causality for the summarization by severity and causal relationship.

The distribution of TEAEs by severity and relationship to the IP will be summarized.

An AE that occurs more than 30 days after the date of the last dose of IP will not be summarized.

The incidence of common ($\geq 2\%$ of patients) TEAEs and AEs leading to premature discontinuation of IP will be summarized by preferred term and will be sorted by decreasing frequency.

An SAE that occurred between the date of the first dose of the open-label IP and 30 days after the date of the last dose of IP, inclusive, will be considered an on-therapy SAE.

The number and percentage of patients who have on-therapy SAEs will be summarized by preferred term. In addition, the incidence of on-therapy SAEs that led to death will be summarized separately by preferred term.

The incidence of AEs leading to premature discontinuation of IP during the OLTP will be summarized by preferred term and will be sorted by decreasing frequency.

Listings will be presented for all patients with SAEs, patients with AEs leading to discontinuation, and patients who die (if any). All patients with SAEs, including SAEs reported during the screening period and the safety follow-up period, and patients discontinuing because of AEs occurring before the start of IP will be included in these listings.

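### After the final visit, nonserious AEs judged unrelated no longer enter the eCRF, so part of the implied 30-day post-dose window is recorded selectively

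*Protocol*

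**What the plan says.** Section 9.5.2.1.4 gives two recording rules. The general rule sends all AEs to the eCRF "whether or not they are considered causally related to the IP". The rule for the 30-day poststudy period is narrower. It begins "Any AEs reported by the patient (or patient representative) during this period are to be recorded in original source documents", and then adds that "AEs are also to be recorded in the eCRF if at least one of the following conditions is met". The first condition is that the event is an SAE. The second is that "the event is judged by the Investigator to be potentially causally related to IP".

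For the length of that period, Section 9.5.2.1.4 refers back to Section 9.5.2.1, where AE collection runs "until 30 days after the final protocol-defined study visit or the last known dose of IP (if the final visit does not occur"). The period therefore starts at the final visit, with the last dose as the fallback start.

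The analysis text counts from a different date. Section 9.7.6.1 states "An AE that occurs more than 30 days after the date of the last dose of IP will not be considered a TEAE", and a little later "An AE that occurs more than 30 days after the date of the last dose of IP will not be summarized". Neither sentence mentions causality. The same section, however, defines both TEAEs and NEAEs as events occurring in the open-label treatment period.

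**The concern.** The recording rule changes at a visit, while the analysis cut-off is set by a dose. Where the two overlap, a nonserious event's presence in the database depends on an open-label causality judgment and on when, or whether, the patient came back. Section 9.5.2.1.1 lets an event be judged unrelated because it is common in the study population or likely due to underlying disease. The restriction therefore removes background nonserious events. All-cause incidence in that stretch can only fall, and the related share can only rise.

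Long-term safety and tolerability is the sole objective, and the study has no control arm in which the same under-recording would also occur. The unrestricted stretch also differs by dosing schedule and by manner of leaving the study, so late nonserious events are not recorded on the same footing across patients.

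**Working it through.** The protocol gives no figure of its own to reproduce. The check is calendar arithmetic.

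**Inputs**
- Last dose, weekly schedule: Section 9.4.7.2 has dosing "from a prefilled single-dose syringe at Visits 2 through Visit 53 (Week 51"), so Week 51.
- Last dose, biweekly schedule: Visit 52, Week 50. This is derived: odd-numbered visits are skipped (Section 9.4.7), and no dosing is planned after Visit 53.
- Final scheduled visit: Visit 55, Week 54 (Section 9.1.2).
- Early discontinuation: an ET visit, then a 2-week follow-up (Sections 9.3.3 and 9.1.3). The gap *e* from last dose to ET visit is not given. I assume 0 to 14 days.
- Analysis cut-off: 30 days after the last dose (Section 9.7.6.1).

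**Formula**

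Day of final visit after last dose: v = 7 × (final-visit week − last-dose week). Restricted days inside the window: f = max(0, 30 − v).

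**Results**
- Weekly completer: v = 7 × (54 − 51) = 21; f = 30 − 21 = 9 days (30%).
- Biweekly completer: v = 7 × (54 − 50) = 28; f = 30 − 28 = 2 days (7%).
- Early termination, ET and follow-up both attended: v = e + 14. For e = 0, f = 16 (53%); for e = 7, f = 9 (30%); for e = 14, f = 2 (7%).
- ET attended, follow-up missed: events reported at the ET visit still fall under the general rule, so f is at most 30 − e, that is 30 down to 16 days.
- No visit after the last dose: the period starts at the last dose, so f = 30 days (100%).

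**Scale against the whole observation period.** Counting from a first dose at Week 0, a weekly completer is observed for 51 × 7 + 1 + 30 = 388 days, and 9/388 = 2.3%. For a biweekly completer it is 50 × 7 + 1 + 30 = 381 days, and 2/381 = 0.5%.

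**Illustration for the cohort.** The protocol expects about 500 entrants and stops at 100 completers, leaving about 400 others. It does not say how many miss the final visit. Let a share m of the 400 miss it with all 30 days restricted, and give everyone else 9 days:

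restricted share = [100 × 9 + 400 × (30m + 9(1 − m))] / (500 × 30)

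- m = 0: 4,500/15,000 = 30%
- m = 0.2: 6,180/15,000 = 41%
- m = 0.5: 8,700/15,000 = 58%

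These are shares of post-dose calendar days under the restriction, not shares of events lost. The values of m are assumptions.

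**What the restriction removes.** SAEs always satisfy the first condition, and nonserious events judged possibly related satisfy the second. Only nonserious events judged unrelated are left out.

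**The case against.** The strongest objection is that the 30-day window for nonserious events is not actually stated. TEAEs and NEAEs are defined as occurring in the open-label period, which ends at Visit 54 (Week 52). The two 30-day sentences only exclude later events; they do not say that everything earlier is counted. The one window expressly defined as last dose plus 30 days is for on-therapy SAEs, which the restriction does not touch. Read literally, a completer's nonserious event after Week 54 is no TEAE, and the 9- and 2-day gaps change no TEAE count. This stands as a limit. But a 30-day exclusion has little purpose unless some events after the open-label period are meant to be summarized, so the window is implied and the text needs aligning either way.

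Four stronger readings are tempting and are not supported.
- A reader might infer that Section 9.5.2.1.4 contradicts itself. It does not: a general rule is followed by an express rule for a later period.
- A reader might infer that the restriction is why patients who do not return have poor capture. The main reason is that querying happens at visits, and no routine query is scheduled afterwards. Among these patients the restriction affects only events they volunteer after being reminded to report.
- A reader might infer that the data are lost for good. Reported events must be in source documents, which monitors can see (Section 9.6.1) and sites must keep for at least 15 years (Section 11.5). Redefining tables would not recover them; entering them from source would.
- A reader might put a number on affected patients. The documents give no rate of missed final visits, so any such count rests wholly on an assumption.

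The study is also descriptive and single-arm, so no treatment comparison is distorted. And Section 9.5.2.1.1 allows a related judgment on timing alone, which makes it easier for events soon after a dose to pass.

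**Conclusion.** The mismatch is real and its effect is modest. Nonserious AEs judged unrelated are kept out of the database for 9 of the 30 post-dose days in weekly completers and 2 of 30 in biweekly completers. The figure is up to 30 of 30 where neither an ET nor a final visit takes place, and fewer where an ET visit is attended after the last dose. For completers this is a small part of follow-up. SAE summaries are unaffected.

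The conclusion rests on two readings: that the poststudy period starts where Section 9.5.2.1 implies, and that the 30-day cut-offs are meant to admit nonserious events after the open-label period. The size of any shift in incidence cannot be derived from the protocol. This is a low-cost improvement to a safety study's data collection and does not invalidate its safety tables.

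**What to change.** In Section 9.5.2.1.4, require every reported AE with onset up to 30 days after the last IP dose to be entered in the eCRF, regardless of seriousness or causality. Apply the serious-or-related restriction only to later onsets. Section 9.5.2.3 already counts pregnancy reporting from the last dose, so the anchor is familiar. Restricted days within the window then become 0 of 30 for every patient, as far as reported events are concerned. The change does not create a query for patients who never return.

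In Section 9.7.6.1, align the TEAE and NEAE definitions with the 30-day cut-off, so that it is clear whether nonserious events after the open-label period count. If the recording rule is kept as it is, the protocol should at least state that nonserious AE summaries after the final visit contain related events only.

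The cost is one sentence in each section, an eCRF completion instruction, and slightly more data entry for events already written in source.
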